11.4 Procedures for Reporting Deviations From the Original Statistical Analysis Plan

If there is any need for a change in the statistical analysis plan, the timing, details and reasons of the change will be included in the clinical trial report.

11.5 Rationale for Target Number of Patients

The number of AML patients is not very high, and is estimated to be approximately 7000 in Japan³⁶. From the fact that in the previous clinical trial (JALSG GML200) in elderly AML patients, it has been forecast that the possible enrollment in Japan is to be at most 70 in one year. Also, from the preliminary trial feasibility survey, it is known that around 50 subjects could be recruited in one year in Republic of Korea and Taiwan. Through a global trial in Japan, Republic of Korea and Taiwan, it is considered possible to enroll 120 subjects in one year to assess the efficacy of OCV-501.

Within the limitation of the past experiences with regard to IMP administration, the target sample size will be considered with reference to following publications^{25,26,27,37}. With reference to disease-free survival which has been reported from trials in AML subjects 60 years or older who have received the consolidation therapy followed by the maintenance therapy, the 2-year DFS rate of placebo arm has been estimated to be around 20%.^{25,26,27} On the other hand, considering the so-called graft-versus-leukemia (GVL) effect associated with a lower relapse risk after the allogeneic hematopoietic stem cell transplantation, OCV-501 is basically expected to have the same benefits. With reference to the findings of Kurosawa et al,³⁷ which have reported a 30% higher 2 or 3-year DFS in elderly AML subjects who have received the allogeneic hematopoietic stem cell transplantation compared with those without transplantation, OCV-501 is expected to have a 15% - 20% higher 2-year DFS. Under the assumption of exponential distribution of DFS time, the hazard ratio (placebo vs. OCV-501) has been set to 0.57 - 0.65, and with a two-sided log-rank test at the 5% significance level, 60 or more subjects in each treatment group can achieve a power of 53 to 75% or more to detect the difference between placebo and OCV-501 groups.

12 Quality Control and Quality Assurance for the Trial

To ensure the quality of the trial, trial sites, contract research organizations, laboratories performing clinical tests, and the sponsor will perform quality control for the trial according to their respective Standard Operating Procedures.

The audit division of the sponsor company will carry out audits within the company and, as necessary, at the trial site and contract research organizations or organizations entrusted to perform related activities, and check whether quality control of the trial is appropriately performed according to the Standard Operating Procedures.

13 General Items of Caution Pertaining to the Trial

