3.2 Rationale for Trial Design

In this trial, the primary endpoint is DFS defined as the time from randomization to AML relapse or death from any cause, whichever comes first within the observation period. This endpoint was set to assess the efficacy of OCV-501 as a maintenance therapy in AML patients who were judged to have achieved CR following an induction regimen. Since DFS is a time-to-event variable, this trial was designed as a randomized comparative study with two treatment arms (the OCV-501 arm and the placebo-control arm). No DLTs were reported and the tolerability of OCV-501 treatment up to a dose of 3 mg was confirmed, and OCV-501 specific DTH was observed at each dose in this phase 1 trial (Trial 311-10-001), and the number of AML patients is not very high. The maximum dose (OCV-501 3 mg) that has been confirmed safe in the phase 1 trials will be used to assess the efficacy and safety of OCV-501 compared with placebo. Since no treatments are administered in patients who complete consolidation therapy, placebo was set as a control.

The DFS rates in maintenance therapy with other drugs^{25,26,27} in AML patients 60 years or older are summarized below. As DFS rates were approximately 10 to 30% after 2 years, approximately 70 to 90% of events could be observed within 2 years. Thus, the observation period of DFS in this trial is set from the time of randomization to 2 years after the first IMP administration.

Disease Free Survival Rates			
Publication	1 year later	2 years later	3 years later
Cancer and Leukemia Group B Study 9720 (2008) ²⁵	29%	10%	5%
Hellstrand et al (2008) ^{26,*}	44%	32%	27%
Cancer and Leukemia Group B study 9420 (2002) ^{27,**}	40%	20%	18%
Note: values are round number			
*Leukemia-free survival: Definition is identical to DFS. Values are estimated by comparing data among all patients and patients less than 60 years of age.			
** Results of Interleukin 2 monotherapy			

Protocol No. 311-12-001

For overall survival (OS), the cutoff date was set as the date after 728 days (2 years) from the day that the last subject started IMP administration

As mentioned above, no DLTs were reported and the tolerability of OCV-501 treatment up to a dose of 3 mg was confirmed, and OCV-501 specific DTH was observed at each dose in the phase 1 trial. This study will consist of two arms (ie, OCV-501 arm and placebo arm) with consideration of feasibility of patient enrollment.

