11.3.1.1 Primary Endpoint

1) Definition

- Disease-free survival (DFS)
 - Observation period: For each subject, the time from randomization to the DFS-cutoff date. The DFS-cutoff date was set as the completion date of each subject.
 - Definition: The time from randomization until relapse or death from any cause, whichever comes first by the DFS-cutoff date.
 - Event: Relapse or death from any cause by the DFS- cutoff date.
 - Censoring:
 - If an event has not been observed by the DFS-cutoff date, then the last confirmed non-relapse date will be used as the censoring date.
 - For subjects who have withdrawn from this trial before the completion date for reasons other than relapses or deaths, if non-relapse has been confirmed on the withdrawal date, then the withdrawal date will be used as the censoring date.

2) Analysis Set

FAS, PPS

3) Analysis Method

Primary method: Kaplan-Meier curve, log-rank test

The Kaplan-Meier method will be carried out to estimate DFS functions and plot the DFS curve by treatment arm.

- The log-rank test will be used to determine whether there are differences at the 5% significance level in DFS between the OCV-501 treatment arm and the placebo arm.
- The hazard ratio (OCV-501 vs. placebo) and its 95% confidence interval will be calculated using the wald test.
- The 2-year survival rate and median survival time will be calculated and 95% CI of survival rate will be calculated using the Greenwood formula.

Exploratory method:

- Harrington-Fleming Test: applying the weight $1-S(t)$, where $S(t)$ is calculated from Kaplan Meier survival estimate.
- HR and its 95% CI will be calculated at every 3-month interval. The hazard rate will be calculated using the person-year method by treatment arm.
- The Cox PH (Proportional Hazards) model will be used to adjust treatment comparison for a set of covariates which are set to be country (each country) and age (60 to 64 years, 65 to 70 years, and ≥ 71 years) on the time-to-event variable. Also, the assumption that the hazard ratio is constant over time will be graphically assessed by looking at the log-minus-log survival plots with stratification of covariates.

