 - In the model of Cox analysis, treatments effect will be adjusted with covariates (Age, Country/Region and WT1 mRNA level at Day 1). The model with covariates (WT1 mRNA only) or model without covariates will be also analyzed. In these models, age will be categorized into 3 groups (60 to 64 years, 65 to 70 years, ≥ 71 years), Country/Region into 2 groups (Japan, Republic of Korea+Taiwan), WT1 mRNA into 4 groups (<50, 50-199, 200<= and Unknown).
 - BRESLOW method will be used for ties.
 - Proportionality assumption in Cox proportional hazard model will be assessed using 2 methods:
 - 1) SAS PHREG procedure ASSESS PH option will be used for checking proportional hazard assumption.
 - 2) Look at the log-minus-log survival plots graphically. If the graph results in parallel lines then the proportionality assumption is satisfied.
- HR and its 95% CI at every 3 months interval will be calculated by adding a time varying covariate to Cox Proportional Hazards model as an alternative analysis if the proportionality assumption fails. The model will be as follows:

$$\lambda(t;X) = \lambda_0(t) \exp(\beta_1 \text{trt} * \text{period}_1 + \beta_2 \text{trt} * \text{period}_2 + \dots)$$

where $\lambda_0(t)$ is the baseline hazard function,

trt is the treatment arm(1= OCV-501 and 0= Placebo) and

$$period_1 = \begin{cases} 1 & \text{if } 0 \leq DFS \text{ time} < 3 \text{ Months} \\ 0 & \text{otherwise} \end{cases}$$

$$period_2 = \begin{cases} 1 & \text{if } 3 \leq DFS \text{ time} < 6 \text{ Months} \\ 0 & \text{otherwise} \end{cases}$$

...

So HR (OCV-501 vs. Placebo) for each period will be calculated as follows:

$$\lambda(\text{OCV-501}|\text{period}_k) = \lambda_0(t)\exp(\beta_k)$$

$$\lambda(\text{Placebo}|\text{period}_k) = \lambda_0(t)$$

$$\text{HR}(\text{OCV-501 vs. placebo}|\text{period}_k) = \lambda_0(t)\exp(\beta_k) / \lambda_0(t) = \exp(\beta_k)$$

$$95\% \text{ CI} : [\exp(\beta_k - 1.96 * \sqrt{\text{Var}(\beta_k)}), \exp(\beta_k + 1.96 * \sqrt{\text{Var}(\beta_k)})]$$

- For exploratory purposes, the incidence rate over the entire follow-up period will be calculated using the person-year method by treatment arm as follows.

- 1) Calculate the number of events and person-year at risk by treatment arm.
- 2) Calculate the incidence rates and its corresponding 95% CI by treatment arm. (1 year is calculated as 365.25 days)

$$\text{Rate} = \frac{\text{Number of events}}{\text{Person - year}}$$

95% CI:

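### Does the reversed label on the design hazard ratio (0.57 to 0.65) in protocol 11.5 and SAP 4.12 undermine the sample-size rationale?

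*Protocol*

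**What the plan says.** Protocol 11.5 builds the design effect in three steps. It takes it that "the 2-year DFS rate of placebo arm has been estimated to be around 20" percent, then that "OCV-501 is expected to have a 15% - 20% higher 2-year DFS", and then, "Under the assumption of exponential distribution of DFS time", it states that "the hazard ratio (placebo vs. OCV-501) has been set to 0.57 - 0.65". With 60 patients per arm and a two-sided 5% log-rank test it quotes power of 53% to 75% or more. SAP 4.12 carries the same text, with the same label.

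The analysis sections run the other way. Protocol 11.3.1.1 states: "The hazard ratio (OCV-501 vs. placebo) and its 95% confidence interval will be calculated using the wald test". Protocol 11.3.1.2 (overall survival) and 11.3.7 (subgroups) name the arms in the same order. SAP 4.7.1.1 fixes the direction algebraically: "trt is the treatment arm(1= OCV-501 and 0= Placebo", and "So HR (OCV-501 vs. Placebo) for each period will be calculated as follows", with the result written as the OCV-501 hazard over the placebo hazard, exp(β).

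The sample-size sections do not say how long each patient is followed for the power calculation. Protocol 3.2 does give the DFS follow-up: "the observation period of DFS in this trial is set from the time of randomization to 2 years after the first IMP administration". Protocol 11.3.1.1 accordingly sets the DFS cutoff patient by patient.

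**The concern.** The same quantity appears in opposite directions within each document. Taken literally, a placebo-to-OCV-501 hazard ratio below 1 means that placebo patients fail more slowly, so the design assumption would favour placebo. If the label reflected the calculation, the trial would have been sized for a harmful effect. If it did not, a later reader might compare the reported hazard ratio with an assumption running in the other direction.

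The power figure beside it adds to the doubt. Expected events, formula, follow-up model and withdrawal allowance are all absent from the paragraph. A reader who cannot trust the label may wonder whether the power was computed for the primary endpoint at all. At stake would be whether 60 per arm supports the stated 53% to 75%.

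**Working it through.** **Inputs.** Placebo 2-year DFS 0.20; OCV-501 2-year DFS 0.35 or 0.40 (15 or 20 points more); exponential times; 60 per arm; two-sided α = 0.05 (protocol 11.5, SAP 4.12). Allocation 1:1 (protocol 3.1.1). DFS follow-up about 2 years per patient (protocol 3.2, 11.3.1.1). No withdrawal is assumed, since the documents give no rate.

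**1. The plan's hazard ratios.** Under exponential times, HR (OCV-501/placebo) = ln S(OCV-501) / ln S(placebo).
- Gain of 15 points: ln 0.35 / ln 0.20 = 0.652
- Gain of 20 points: ln 0.40 / ln 0.20 = 0.569

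These round to the printed 0.65 and 0.57. The inverses, placebo over OCV-501, are 1.53 and 1.76. Reading the gain as relative would put OCV-501 at 23% to 24% (0.20 × 1.15, 0.20 × 1.20), giving ratios of about 0.91 and 0.89, so the absolute reading is the one that was used.

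**2. What the literal label would imply.** Holding placebo at 0.20 and taking placebo/OCV-501 = 0.57 or 0.65, OCV-501 2-year DFS would be 0.20^(1/0.57) = 5.9% or 0.20^(1/0.65) = 8.4%. The same paragraph expects 35% to 40%. The literal reading contradicts its own inputs, so it cannot be what was calculated.

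**3. Whether the label enters the power.** Schoenfeld: power = Φ(½ · √E · |ln HR| − 1.96). For a given number of events E, only |ln HR| matters, so a ratio and its inverse give the same answer.
- E = 60 × 0.80 + 60 × 0.65 = 87; power = 51.3% at HR 0.652
- E = 60 × 0.80 + 60 × 0.60 = 84; power = 73.3% at HR 0.569

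**4. Whether 53% to 75% can be recovered.** The results above are 1.7 points low at each end. The placebo rate is given only as approximate. At 18.5%, keeping the gains of 15 and 20 points, the ratios are ln 0.335 / ln 0.185 = 0.648 and ln 0.385 / ln 0.185 = 0.566, which still round to 0.65 and 0.57.
- E = 60 × 0.815 + 60 × 0.665 = 88.8; power = 53.3%
- E = 60 × 0.815 + 60 × 0.615 = 85.8; power = 75.1%

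**5. An alternative basis.** Suppose instead 1 year of uniform accrual and a common cutoff 2 years after the last entry. Then P(event) = 1 − (e^(−2λ) − e^(−3λ))/λ with λ = −ln S/2. Expected events are 95.4 and 92.5. The Freedman formula, Φ(√E · (1 − HR)/(1 + HR) − 1.96), gives 53.8% and 75.2%; Schoenfeld gives 55.0% and 77.3%. Both bases come close to the quoted range, so the match alone does not identify which was used.

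**The case for a change.** The best case for acting is that a prespecified design parameter ought to be right as printed. The slip sits in both controlling documents, the SAP gives the ratio an explicit algebraic direction elsewhere, and the repair is a few words. Someone who followed the label literally, with placebo held at 20%, would obtain 104 and 103 events and power of 81.9% and 58.9%, and would fail to verify the plan. On the power basis, the common-cutoff fit resembles the SAP's reference endpoint (DFS followed to the overall-survival cutoff) more than the primary one. With 2 years per patient and exactly 20% on placebo, the calculations fall slightly short of the quoted figures, so the words *or more* are not demonstrated.

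The inversion itself stands. The consequences do not. The 81.9% and 58.9% need a reader to discard the 35% to 40% stated just before the label. Keep those rates and invert the ratio instead, and it is placebo that becomes absurd, at 0.35^0.65 = 51% or 0.40^0.57 = 59%. Neither set describes an assumption of this trial, so neither measures an error.

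On power, the distribution, rates, ratio, test, α and arm size are stated, and the follow-up is in protocol 3.2 and 11.3.1.1. A gap of 1.7 points against an approximate placebo rate cannot discriminate between formulas or show that the wrong endpoint was used. What remains is that the formula, event count and withdrawal allowance are not printed.

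**Conclusion.** A clerical slip with no gain from changing the plan. The numbers 0.57 to 0.65 are correct as OCV-501 over placebo, the surrounding sentences leave no doubt about the direction, and the analysis sections of both documents already use it. Any analyst comparing the result with the design assumption will read it that way.

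The effect on sample size, power, planned analysis and conclusions is nil. The quoted power is consistent with the primary endpoint's own follow-up: 51.3% and 73.3% at a placebo rate of 20%, 53.3% and 75.1% at 18.5%. This rests on exponential DFS, 2 years of follow-up for every patient and no loss to withdrawal. The documents give no withdrawal rate, so no size can be put on that last assumption. Printing the power formula and expected events would be a reporting courtesy. In a trial that calls itself exploratory and rests its size openly on what can be recruited in a year, it would not alter any decision.

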13.1 Ethics and GCP Compliance

This trial must be conducted in compliance with the ethical principles outlined in the Declaration of Helsinki, the ICH-GCP Guideline,^b all applicable regional regulatory requirements (eg, Pharmaceutical Affairs Law, Standards for the Conduct of Clinical Studies [Ordinance No. 28, GCP dated 27 Mar 1997] and related notifications in Japan), and the protocol.

13.2 Institutional Review Board

Each trial site will seek approval from an IRB/IEC according to regional regulations. The IRB/IEC will investigate the ethical, scientific, and medical appropriateness of the trial. Further, in preparing and handling eCRFs, the investigator, subinvestigator, and their staff must take measures to ensure adequate care in protecting subject privacy.

13.3 Subject Consent

13.3.1 Procedures for Obtaining Consent

- 1) Prior to the start of the screening examination, the investigator or subinvestigator will fully explain the matters listed in Section 13.3.2 to each subject who will be included in the trial, using the ICF, and give the ICF to the subject. The subject will be provided sufficient time to make a decision regarding participation. After confirming that the subject has properly understood the explanation, the investigator or subinvestigator will obtain written voluntary consent for participation in the trial from the subject.
- 2) The investigator or subinvestigator who has provided the explanation and the subject will each put their printed name and personal seal or signature on the ICF, and write the date on which they sign or stamp the form. If a trial associate has provided a supplemental explanation of the trial, he/she will also put his/her printed name and personal seal or signature on the form and write the date on which he/she signs or stamps the form.
- 3) The original of the ICF that was signed or stamped and dated will be retained by the investigator or subinvestigator according to the regulations of the trial site. A copy of the original ICF will be given to the subject.
- 4) After obtaining informed consent from a subject, the investigator or subinvestigator will write the date of informed consent acquisition and subject number in the documents for enrolled subjects (list of screened subjects and list of enrolled subjects).

^b International Conference on Harmonization (ICH) [homepage on the Internet]. E6: Good Clinical Practice: Consolidated Guideline [finalized May 1996, corrected Jun 1996; cited 2005 Dec 06]. Available from: <http://www.ich.org/cache/compo/276-254-1.html>.

- 5) If new information becomes available that may influence the willingness of the subject to continue participation in the trial, the investigator or subinvestigator will promptly inform the subject of such information and confirm the willingness of the subject to continue participation in the trial, and then record the result in the subject's medical records. If there is guidance regarding the recording of re-consent stipulated by the trial site, it will be followed.

13.3.2 Contents of Informed Consent Form

The informed consent form must explain the following:

- 1) That the trial involves research
- 2) The purpose of the trial
- 3) The trial treatment(s) and the probability for random assignment to each treatment
- 4) The trial procedures to be followed, including all invasive procedures
- 5) The characteristics of HLA genotyping
- 6) The subject's responsibilities
- 7) Those aspects of the trial that are experimental
- 8) The reasonably foreseeable risks or inconveniences to the subject and, when applicable, to an embryo, fetus, or nursing infant
- 9) The reasonably expected benefits. When there is no intended clinical benefit to the subject, the subject should be made aware of this.
- 10) The alternative procedure(s) or course(s) of treatment that may be available to the subject, and their important potential benefits and risks
- 11) The compensation and/or treatment available to the subject in the event of trial-related injury
- 12) The anticipated prorated payment, if any, to the subject for participating in the trial
- 13) The anticipated expenses, if any, to the subject for participating in the trial.
- 14) That the subject's participation in the trial is voluntary and that the subject may refuse to participate or withdraw from the trial, at any time, without penalty or loss of benefits to which the subject is otherwise entitled.
- 15) That the monitor(s), the auditor(s), the IRB/IEC, and the regulatory authority(ies) will be granted direct access to the subject's original medical records for verification of clinical trial procedures and/or data, without violating the confidentiality of the subject, to the extent permitted by the applicable laws and regulations and that, by signing a written informed consent form, the subject or the subject's legally acceptable representative is authorizing such access
- 16) That records identifying the subject will be kept confidential and, to the extent permitted by the applicable laws and/or regulations, will not be made publicly available. If the results of the trial are published, the subject's identity will remain confidential.

- 17) That the subject or the subject's legally acceptable representative will be informed in a timely manner if information becomes available that may be relevant to the subject's willingness to continue participation in the trial
- 18) The person(s) to contact for further information regarding the trial and the rights of trial subjects, and whom to contact in the event of trial-related injury
- 19) The foreseeable circumstances and/or reasons under which the subject's participation in the trial may be terminated
- 20) The expected duration of the subject's participation in the trial.
- 21) The approximate number of subjects involved in the trial

13.3.3 Amendments to the Informed Consent Form

If revision of the ICF becomes necessary due to newly obtained information, the investigator will promptly revise the ICF to include that information after conferring with the sponsor.

The investigator, when revising the ICF, will report this to the head of the trial site and submit the revised document to the IRB designated by the trial site to obtain its approval.

If new information becomes available that may influence the willingness of subjects to continue participation in the trial and the ICF has been revised according to the new information, the investigator or subinvestigator will again obtain subjects' written informed consent to continue participation in the trial.

13.4 Management of Investigational Medicinal Products

- 1) The sponsor will issue the "Procedures for Handling of Investigational Medicinal Products" to the head of the trial site and the IMP manager designated by the head of the trial site (referred to as the IMP manager hereinafter).
- 2) The sponsor will issue the "Document on Investigational Medicinal Products Storage Conditions" to the investigator or subinvestigator, trial associates, and IMP manager.
- 3) The sponsor will deliver the IMPs to the trial site following the start of the trial period contracted with the trial site.
- 4) The IMP manager will manage the IMPs appropriately according to the "Procedures for Handling of Investigational Medicinal Products" prepared by the sponsor.
- 5) The IMP manager will prepare and retain the "Record of Management and Storage of Investigational Medicinal Products."

